### 6.3. Multi-Center Studies

This is a multi-center study enrolling subjects from 49 US sites. The number of subjects per site might be small. Therefore, there are no analyses adjusting for sites.

### 6.4. Multiple Comparisons / Multiplicity

To control the overall Type I error rate across the seven hypothesis tests involving the primary endpoint and the key secondary endpoints (listed below) at the 0.05 level (two-sided), a fixed sequence procedure will be implemented. The hypothesis tests will be assessed sequentially as follows:

1. Noninferiority of 0.002% DE-117 to 0.5% timolol maleate for the primary endpoint, IOP at each scheduled timepoint (08:00, 10:00, and 16:00) at Week 1, Week 6, and Month 3.
2. Noninferiority of 0.002% DE-117 to 0.5% timolol maleate for the first key secondary endpoint, mean diurnal IOP at Month 3.
3. Noninferiority of 0.002% DE-117 to 0.5% timolol maleate for the second key secondary endpoint, IOP at each scheduled timepoint (08:00, 10:00, and 16:00) at Week 1, Week 6, and Month 3 in the study eyes with mean diurnal IOP < 25 mmHg at the Baseline Visit.

4. Superiority of 0.002% DE-117 to 0.5% timolol maleate for the third key secondary endpoint, mean diurnal IOP at Week 1.
5. Superiority of 0.002% DE-117 to 0.5% timolol maleate for the first key secondary endpoint, mean diurnal IOP at Month 3.
6. Superiority of 0.002% DE-117 to 0.5% timolol maleate for the second key secondary endpoint, IOP at each scheduled timepoint (08:00, 10:00, and 16:00) at Week 1, Week 6, and Month 3 in the study eyes with mean diurnal IOP < 25 mmHg at the Baseline Visit.
7. Superiority of 0.002% DE-117 to 0.5% timolol maleate for the primary endpoint, IOP at each scheduled timepoint (08:00, 10:00, and 16:00) at Week 1, Week 6, and Month 3.

The second hypothesis testing 2) will be tested only if the first hypothesis 1) is rejected. The third hypothesis testing 3) will be tested only if the second hypothesis 2) is rejected, and so on.

## 6.5. Interim Analysis

No interim analysis is planned for this study.

Analysis of the double-masked period data will be conducted when all the randomized subjects complete their Month 3 Visit, data cleaned and frozen. All efficacy and safety data from open-label period at the time of this data cut will also be analyzed and reported. The [011709IN Data Cut Plan](#) details how data collected during open-label period will be cut for this “snapshot”.

## 7. SUMMARY OF STUDY POPULATION DATA

### 7.1. Subject Disposition

The disposition of ITT population (i.e., all randomized subjects) will be summarized by treatment period (double-masked and open-label) and by planned treatment (for double-masked period) and overall.

For the double-masked period, the summary will include the number and percentage of ITT subjects in the Safety population, FAS, and PPS. The disposition summary will also include the number and percentage of subjects who completed the study drug, subjects who discontinued the study drug prematurely but continued with study participation until the Month 3 Visit and among which who completed or not completed the Month 3 Visit, as well as the number and percentage of subjects who discontinued from the study or discontinued from the study drug prior to Month 3 Visit by the primary discontinuation reason.

For the open-label period, the summary will include the number and percentage of subjects who received any study treatment during open-label period, and subjects who are still on the study at the time of data cut (for reports other than the final clinical study report). The disposition summary will also include the number and percentage of subjects who completed the study drug, and subjects who discontinued from the study prior to Month 12 Visit by the primary discontinuation reason.

### 7.2. Demographics and Baseline Characteristics

Subject demographics and baseline characteristics will be descriptively summarized for the FAS, adult subjects, pediatric subjects, Safety population, and subjects who received open-label treatment period therapy with DE-117, separately, by planned treatment (for double-masked period). Specifically, for subject demographics, the following variables will be summarized:

- Age at randomization (continuous and categorical: < 18 years,  $\geq$  18 and < 65 years, or  $\geq$  65 years)
- Sex (categorical: Male or Female)
- Ethnicity (categorical: Hispanic/Latino or Not)
- Race (categorical: American Indian or Alaska Native, Asian, Black or African American, Native Hawaiian or Other Pacific Islander, White, or Other)

For baseline characteristics, the following variables will be summarized for study eye and fellow eye, separately by treatment period (double-masked and open-label):

- Primary ocular diagnosis [categorical: POAG, Pseudoexfoliative Glaucoma, Pigmentary Glaucoma, or OHT for adult subjects, and juvenile open angle glaucoma (JOAG) for pediatric subjects]
- Prior use of IOP-lowering medications (categorical: oral/topical carbonic anhydrase inhibitors, alpha agonists, beta-blockers, prostaglandin/prostaglandin analogues, or none)
- Prostaglandin naive (Yes or No)

- Baseline lens status (categorical: phakic or pseudophakic/aphakic)
- Baseline mean diurnal IOP score and baseline IOP score at each scheduled timepoint (08:00, 10:00, and 16:00)
- BCVA (logMAR)
- Central corneal thickness (μm)
- Glaucomatous optic nerve findings (categorical: none, mild, moderate, or severe)
- Anterior chamber angle classification (Shaffer scale; categorical: approximately 5 degrees or less, approximately 10 degrees, approximately 20 degrees, approximately 30 degrees, or approximately 40 degrees or more)
- Iris Color (categorical: Blue/Gray, Blue/Gray with Slightly Brown, Blue/Gray – Brown, Green, Green with Slightly Brown, Green – Brown, Yellow – Brown, or Brown)
- Visual field (parameters: glaucoma Hemifield test, visual field mean deviation by device, and visual field pattern standard deviation by device)

### **7.3. Medical and Surgical History**

For this study, medical and surgical history and adverse events will be coded using MedDRA 21.1, 2018. Each medical event will be classified into a SOC and mapped to a Preferred Term (PT).

The medical and surgical history will be summarized for the FAS. Subjects reporting any medical and surgical history at baseline will be tabulated by SOC and PT for each planned treatment and overall.

### **7.4. Protocol Deviations**

In this study, protocol deviations are categorized as follows:

- Informed consent
- Inclusion/exclusion criteria
- Concomitant treatment
- Investigational product
- Procedures/tests/assessments
- Laboratory
- Randomization
- Safety reporting
- Time Window
- Other

A protocol deviation is considered significant if it may affect the subject's rights, safety, or well-being, and/or the completeness, accuracy, or reliability of the study data. Santen's study team will review all protocol deviations and determine the list of significant protocol deviations prior to database lock. All randomized subjects with any significant protocol deviation(s) will be tabulated by treatment period (double-masked and open-label) and by deviation category for each planned treatment (for double-masked period) and overall. In addition, two listings will be provided for double-masked period: (1) all significant protocol deviations and (2) subjects excluded from the per protocol population. All significant protocol deviations will also be listed for open-label period.

## 7.5. Prior and Concomitant Medications

For this study, non-study medications, including prior and concomitant medications for double-masked period and concomitant medications for open-label period, will be coded using World Health Organization (WHO) Drug Global, Version September 2018, format B3. Each non-study medication will be classified using the Anatomical-Therapeutic-Chemical (ATC) classification system and mapped to a WHO Drug preferred drug name.

Non-study medications will be summarized for the Safety population. Subjects taking any prior medications will be tabulated by ATC level 3, level 4, and preferred drug name for each actual treatment received and overall. A subject will be counted at most once for each prior medication, even if the subject took the same prior medication on multiple occasions. Subjects taking any concomitant medications will be tabulated similarly. In addition, prior medications and concomitant medications will also be listed, separately.

For the same concomitant medications that are used in both double-masked and open-label treatment periods, they will be summarized in both double-masked and open-label periods.

## 7.6. Treatment Compliance

For the purpose of compliance calculation, there will be six study intervals:

- Baseline Visit to Week 1
- Week 1 to Week 6
- Week 6 to Month 3
- Month 3 to Month 6
- Month 6 to Month 9
- Month 9 to Month 12

The compliance rate for a subject will be calculated as follows for each study interval during double-masked period:

$$\text{Compliance Rate (\%)} = (2 * \text{Duration} - \sum \text{Miss}) / (2 * \text{Duration}) \times 100$$

And, for open-label period:

$$\text{Compliance Rate (\%)} = (\text{Duration} - \sum \text{Miss}) / (\text{Duration}) \times 100$$

Where

Duration: The number of days subject should have administered study medication, calculated as:

| Study Interval           | Equation for Duration Calculation                   |
|--------------------------|---|
| Baseline Visit to Week 1 | Week 1 Visit date – Date of first drug dispensation |
| Week 1 to Week 6         | Week 6 Visit date – Week 1 Visit date               |
| Week 6 to Month 3        | Month 3 Visit date – Week 6 Visit date              |
| Month 3 to Month 6       | Month 6 Visit date – Month 3 Visit date             |
| Month 6 to Month 9       | Month 9 Visit date – Month 6 Visit date             |
| Month 9 to Month 12      | Month 12 Visit date – Month 9 Visit date            |

Miss: The number of missed doses since the last visit.

For subjects in the FAS, the compliance rate will be summarized by treatment period (double-masked and open-label), post-baseline study interval, and by planned treatment (for double-masked treatment period).

## 7.7. Exposure to Study Medication

The duration of exposure to a study medication is measured by days on treatment as derived in [Section 4.1.5](#). For subjects in the Safety Population, the duration of exposure will be summarized using descriptive statistics, and frequency and percentage of subjects will be tabulated by actual treatment received for double masked period and for the entire study separately. For the entire study period, the duration of exposure to overall DE-117 treatment will also be provided, which will combine exposure to DE-117 from both double-masked arms. For subjects who were in the Timolol arm during double-masked treatment period, their duration of exposure to DE-117 will be the total duration on the study minus the number of days they were exposed to Timolol treatment.

The duration of exposure categories are:

- Double-masked period: 1-30, 31-60, or  $\geq 61$  days
- Entire study period: 1-30, 31-60, 61-90, 91-120, 121-150, 151-180, 181-210, 211-240, 241-270, 271-300, 301-330, or  $\geq 331$  days

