### **3.4. Visits and Assessments**

There are 5 scheduled visits for pediatric subjects and 9 scheduled visits for adult subjects. Assessments at each visit and the time/visit window for each post-baseline assessment are specified in the Assessment Schedule for adult ([Table 1](#)) and pediatric subjects ([Table 2](#)), respectively.

If the study drug administration is discontinued prior to Visit 5 (end of the double-masked treatment period), the subject should be encouraged to still participate in follow-up study visits until Visit 5 on an observational basis. For subjects whose study participation is terminated prior to Visit 8 (Month 12), to the extent possible, all assessments scheduled for Visit 8 (Month 12) will be performed at the Exit Visit.

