**Table 3: Definitions for Treatment Start and End Dates by Treatment Period**

| Treatment Period                    | Treatment Start Date   | Treatment End Date   |
|-------------------------------------|--|--|
| Double-Masked (DM) Treatment Period | The date at which a randomized subject takes the first dose of the DM study drug       | 
The date at which a randomized subject takes the last dose of the DM study drug. If the date of the last dose is missing and the subject does not receive any OL study drug:
 
 
• The day before the Visit 5 (Month 3) date will be considered the treatment end date for subjects who completed the Month 3 Visit
 
• The day before the Exit Visit date will be used for subjects who prematurely discontinued from the study before Visit 5 (Month 3). If the Exit Visit date of a non-completer is not available, then the day before the last available visit date will be considered the treatment end date
 
 |
| Open-Label (OL) Treatment Period    | The date at which a randomized adult subject takes the first dose of the OL study drug | 
The date at which a randomized adult subject takes the last dose of the OL study drug. If the date of the last dose is missing:
 
 
• The day before the Visit 8 (Month 12) date will be considered the treatment end date for subjects who completed the Month 12 Visit
 
• The day before the Exit Visit date will be used for subjects who prematurely discontinued from the study during OL period. If the Exit Visit date of a non-completer is not available, then the day before the last available visit date will be considered the treatment end date
 
  |

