**Table 3: Definitions for Treatment Start and End Dates by Treatment Period (Continued)**

| Treatment Period | Treatment Start Date   | Treatment End Date   |
|------------------|--|--|
| Entire Study     | The date at which a randomized subject takes the first dose of the DM study drug | The date at which a randomized subject takes the last dose of the study drug.
Missing last dose date will be handled the same way as mentioned above. |

Notes:

1. Pediatric subjects only participate in the double-masked period.
2. For each treatment period, the treatment end date will be set to missing if the treatment start date is missing.

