#### 4.1.5. Extent of Exposure

The *extent of exposure* to study medication will be assessed by duration of treatment exposure, derived as:

$$\text{Duration of treatment exposure} = \text{Treatment end date} - \text{Treatment start date} + 1$$

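### SAP 7.7 derives DE-117 exposure in the Timolol arm by subtraction from an undefined study duration, so off-drug time can be reported as DE-117 exposure

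*SAP*

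**What the plan says.** SAP 7.7 starts from a general rule, with a pointer to Section 4.1.5: "The duration of exposure to a study medication is measured by days on treatment as derived in" that section. There, exposure "to study medication will be assessed by duration of treatment exposure, derived as" end date minus start date plus 1.

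For the combined DE-117 summary over the entire study, 7.7 then gives the Timolol arm its own rule, under which a subject's DE-117 exposure "will be the total duration on the study minus the number of days they were exposed to Timolol treatment". The SAP does not define total duration on the study, and nothing restricts the sentence to subjects who entered open label.

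Three other places bear on this:

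- **SAP 3.4.** If study drug is stopped before Visit 5, "the subject should be encouraged to still participate in follow-up study visits until Visit 5 on an observational basis". Protocol 7.4.6 and 8.5 say the same.
- **SAP 7.1.** The disposition table counts as a separate group "subjects who discontinued the study drug prematurely but continued with study participation until the Month 3 Visit".
- **SAP Table 3.** The open-label start is "The date at which a randomized adult subject takes the first dose of the OL study drug", with a matching end date. A separate row for the entire study ends at "The date at which a randomized subject takes the last dose of the study drug".

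**The concern.** The plan deliberately keeps some subjects on study after they stop drug, and SAP 7.1 recognises that time on study and time on drug differ. The 7.7 subtraction removes only Timolol days. Whatever remains is labelled DE-117 exposure, whether or not DE-117 was being taken. This covers observation after an early Timolol stop and the interval between the last open-label dose and the exit visit. Pediatric Timolol subjects, up to 15 as planned, cannot receive DE-117 in this study at all, yet the sentence does not exclude them.

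What is at stake is the accuracy of the table describing overall exposure to DE-117, including how many subjects appear in each duration category. The table would also not match the adverse-event rule in SAP 9.1. For Timolol-arm subjects, that rule admits to the overall DE-117 column only events that began in the open-label period. Under 7.7, off-drug days before open label could enter exposure while events starting on those same days stay out.

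**Working it through.** The plan states no figure on this point, so there is nothing to reproduce. The check is date arithmetic on illustrative Timolol-arm subjects.

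**Inputs from the documents.** First dose is on Day 1. Visit 5 has target Day 91 and Visit 8 has target Day 361. Open-label dosing starts on the evening of Visit 5 and ends the evening before Visit 8 (Protocol 7.1), so a completer doses open label on Days 91–360. The exposure formula is in SAP 4.1.5 and the period dates are in Table 3.

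**Assumed.** The early stopping days and the Day 195 exit.

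**Three derivations of DE-117 days.**

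- A, literal 7.7: (last study day − first dose day + 1) − Timolol days.
- B, Table 3 entire-study span: (last dose day of any study drug − first dose day + 1) − Timolol days.
- C, direct: open-label end − open-label start + 1, or 0 with no open-label dose.

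| Subject | Timolol days | A | B | C |
|---|---|---|---|---|
| Stops Day 20, observed to Day 91, no open label | 20 | 91 − 20 = 71 | 20 − 20 = 0 | 0 |
| Stops Day 43, observed to Day 91, no open label | 43 | 91 − 43 = 48 | 43 − 43 = 0 | 0 |
| Timolol to Day 91, open label Days 91–181, exit Day 195 | 91 | 195 − 91 = 104 | 181 − 91 = 90 | 181 − 91 + 1 = 91 |
| Stops Day 43, open label Days 91–360, exit Day 361 | 43 | 361 − 43 = 318 | 360 − 43 = 317 | 360 − 91 + 1 = 270 |
| Completer: Timolol to Day 91, open label Days 91–360, exit Day 361 | 91 | 361 − 91 = 270 | 360 − 91 = 269 | 360 − 91 + 1 = 270 |

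Under A, the first two subjects enter the 61–90 and 31–60 day categories without having taken DE-117. B corrects both but still credits the off-drug gap in the fourth row: 317 − 270 = 47 days too many. If the undefined term were taken to start at consent, A would also add up to 35 screening days.

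**Mismatch with SAP 9.1.** In the fourth row, Day 60 counts as DE-117 exposure under A and B. An adverse event starting on Day 60 is not counted in the overall DE-117 column, because it began before open label.

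**Scale, by assumption.** The documents give no rate of early Timolol stopping with continued observation. If 5–10% of 200 did so on the Day 20 pattern, that is 10–20 subjects and 10 × 71 = 710 to 20 × 71 = 1,420 days. Planned adult DE-117 exposure with full retention is 200 × 360 + 200 × 270 = 126,000 subject-days. The excess is 710 / 126,000 = 0.6% to 1,420 / 126,000 = 1.1%.

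**The case against.** The best defence is context. The paragraph opens by measuring exposure as days on treatment, the disputed sentence concerns the entire study period, and Table 3 has a row for exactly that period, running from first to last dose. On that reading (B) a subject who never took DE-117 gets 0, and 0 falls in no category because the categories start at 1–30 days. This may well be what was intended, so the 71-day result depends on the literal reading. It does not settle the point. The sentence refers to time on the study and does not cite Table 3, and SAP 7.1 treats study participation and study drug as different things.

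The gap that B would still count is also conditional. The protocol converts adults to open label after they complete the double-masked period. No section describes an early Timolol stopper starting open-label drug, though none rules it out. The Table 3 span counts gaps in the DE-117 arm too. There, however, the gap lies within a course of the same drug; in the Timolol arm it is assigned to a drug not yet started.

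A reader might infer two stronger things that the documents do not support:

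- **That inflated exposure dilutes adverse-event frequency.** SAP 9.1 tabulates subjects, each counted once per system organ class or preferred term. It plans no rates per unit of exposure, and nothing ties the overall DE-117 adverse-event column to the 7.7 subtraction.
- **That every completer is one day short.** The 269 arises only under B; the literal rule gives 270. The difference is a convention about the Visit 5 date, when the morning dose is masked drug and the evening dose is open label. The 71-day and 269-day results come from different readings and cannot both apply.

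**Conclusion.** The point holds, and it is minor. Followed literally, SAP 7.7 gives a wrong DE-117 exposure for any Timolol-arm subject with off-drug time on study, including subjects who never took the drug. Under the more generous reading, the error shrinks to gaps before open label, if such subjects exist. The sentence does not say which reading applies, and the direct calculation from open-label dates avoids both problems.

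The consequence is limited to one descriptive table and its mismatch with the SAP 9.1 event window. Efficacy inference is untouched. The stopping days are illustrative, and the 0.6–1.1% rests on the assumed 5–10% rate, the literal reading, observation to Day 91 and full retention in the comparison total.

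**What to change.** Replace the Timolol-arm sentence in SAP 7.7 with a direct derivation. For these subjects, DE-117 exposure is the open-label treatment end date minus the open-label treatment start date plus 1, using the Table 3 dates and the Section 4.1.5 formula. Subjects with no open-label dose, including all pediatric Timolol subjects, have no DE-117 exposure and are left out of the overall DE-117 exposure summary.

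The cost is one sentence. Table 3 already defines both dates, including the handling of a missing last dose, so no new data are needed. For a subject who takes both drugs on the Visit 5 date, that day counts once for each drug; a table footnote can say so. The reported exposure then covers the same period as the events counted under SAP 9.1 for these subjects.

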## 8. EFFICACY ANALYSES

Unless specified otherwise, efficacy analyses will be performed on the study eye, based on the FAS, and summarized by planned treatment, irrespective of the actual treatment received.

Unless otherwise specified, for subjects who receive IOP-lowering rescue therapy, any IOP values collected after the receipt of rescue therapy will be censored (i.e., treated as missing) in the analyses.

### 8.1. Efficacy Analyses for Double-Masked Period

#### 8.1.1. Analyses of Primary Endpoint and Key Secondary Endpoints

##### 8.1.1.1. Primary Analyses

###### 8.1.1.1.1. Primary Endpoint

The primary efficacy endpoint is IOP in the study eye at each scheduled timepoint (08:00, 10:00, and 16:00) at each of three follow-up visits, Week 1, Week 6, and Month 3. The nine combinations of three scheduled timepoints at each of three follow-up visits are referred to subsequently as nine timepoints. For the primary endpoint, the following null (versus alternative) hypothesis will be tested:

$$H_0: \mu_T - \mu_C > \Delta \text{ for at least one timepoint}$$

versus

$$H_A: \mu_T - \mu_C \leq \Delta \text{ at all nine timepoints}$$

where  $\mu_T$  and  $\mu_C$  denote the mean values of the primary endpoint in the DE-117 arm and the Timolol arm, respectively, and  $\Delta$  denotes the noninferiority margin of 1.5 mmHg or 1.0 mmHg as specified below.

The primary analysis of the primary efficacy endpoint will be performed using a MMRM of IOP based on the FAS. A separate MMRM will be used for IOP at each scheduled timepoint (8:00, 10:00, or 16:00). For each scheduled timepoint, the model will include treatment ( $T_i$ ), analysis visit ( $V_j$ ), and treatment-by-visit interaction ( $TV_{ij}$ ) as fixed effects, and baseline IOP at the scheduled timepoint as a covariate. Correlations of IOP measurements within-subject will be modeled using an unstructured covariance matrix. The mathematical model is given by:

$$IOP_{ijn} = \mu + T_i + V_j + TV_{ij} + \varepsilon_{ijn}$$

where  $\mu$  denotes the overall mean, and  $\varepsilon$  denotes the random error associated with the individual subject. The above model allows treatment effect and its variability to vary over study visits.

If there are convergence issues, covariance matrix structures other than unstructured will be tried in the following order: (1) heterogeneous Toeplitz (TOEPH), (2) heterogeneous autoregressive of order 1 (ARH(1)), (3) heterogeneous compound symmetry (CSH), and (4) compound symmetry (CS). The first covariance structure that converges will be used as the primary analysis. Least squares mean IOP values for each treatment arm and differences between least squares treatment arm means and associated 95% confidence intervals will be reported for each of the nine timepoints.

The primary analysis will be repeated on pediatric subjects.

**Noninferiority criteria for primary endpoint:** With respect to the primary study objective, noninferiority of DE-117 to Timolol is achieved if the upper limit of the two-sided 95% confidence interval for the difference in the mean IOP (DE-117 minus Timolol) is  $\leq 1.5$  mmHg at all nine timepoints and  $\leq 1.0$  mmHg at a majority (five or more) of the nine timepoints.

Superiority of DE-117 to Timolol for the primary efficacy endpoint is achieved if the upper limit of the two-sided 95% confidence interval for the difference in the mean IOP (DE-117 minus Timolol) is  $< 0$  mmHg at all nine timepoints.

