9.4. Randomization and Masking

A stratified permuted-block randomization will be employed to randomize eligible subjects in a 1:1 ratio to either DE-117/Vehicle arm or Timolol Maleate arm. Two strata will be constructed based on age (adult: ≥ 18 years; pediatric: < 18 years).

The randomization schedule will be generated and implemented using central randomization via Interactive Response Technology (Medidata BALANCE). Each randomized subject will receive numbered study medication kits as assigned by BALANCE.

This is a double-masked study through Month 3. The subjects, Investigators, Examiners and Santen personnel involved in the conduct of the study will be masked to the study treatment. An authorized unmasked study staff member who is not the Investigator or Examiner at the investigative site will dispense and collect study medication(s) and will query about dosing compliance. Subjects will be instructed not to show the eye drop bottles or discuss the eye drop to either the Investigator or the Examiner or other study subjects. The active control treatment (Timolol Maleate) containers will be over-labeled and packaged in the same secondary package (e.g., cardboard carton) as the investigational treatment (DE-117). All subjects will receive a bottle labeled "morning" for the morning dose and a bottle labeled "evening" for the evening dose.

At the completion of the Visit 5 (Month 3) procedures, the adult subjects will be dispensed open-label DE-117 Ophthalmic Solution 0.002% and instructed to dose once daily in both eyes at 20:00 for the duration of the study.

In case of a medical emergency, the Principal Investigator may reveal the treatment information by unmasking through Medidata BALANCE to know which treatment the subject has received. The Principal Investigator (or his/her designee) should contact Santen, or Santen's designee, before taking this measure, if there is sufficient time. Santen, or Santen's designee, must be informed of all instances where the code is broken and of the reasons for such instances.

[figure not shown]
Additionally, the AE or SAE for which study treatment was unmasked should be reported to Santen Pharmacovigilance.

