### **3.3. Sample Size Planning**

The sample size calculation was based on a two-sided Type I error rate of 5% and a non-inferiority margin of 1.5 mmHg. Assuming a treatment difference of 0 mmHg between the DE-117 arm and the Timolol arm, a standard deviation (SD) of 4.0 mmHg, and a correlation coefficient of 0.6 among repeated measures, approximately 400 adult subjects in total (200 subjects per treatment arm) will provide 90% power to demonstrate noninferiority of DE-117 Ophthalmic Solution 0.002% to Timolol Maleate Ophthalmic Solution 0.5% in IOP-lowering effect. Up to 30 pediatric subjects will be enrolled with the agreement from FDA.

The standard deviation of 4.0 mmHg was determined from previous DE-117 studies conducted in the United States: 33-002 and 33-003.

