### **5.3. Full Analysis Set**

The Full Analysis Set (FAS) will include all randomized subjects who received at least one dose of study medication and provided Baseline IOP data (at any timepoint) and at least one post-baseline IOP measurement (at any timepoint). Efficacy analyses will be performed using the FAS and summarized by treatment as randomized.

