### 6.1. Adjustments for Covariates

In general, the inferential analysis of each IOP endpoint will adjust for the baseline IOP. Detailed information on covariate adjustment is provided in [Section 8.1](#).

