#### 8.1.1.2. Sensitivity Analyses

For the primary endpoint and the key secondary endpoints, sensitivity analyses will be performed to assess the robustness of the results from the primary analysis. The sensitivity analyses consist of two types: (1) assessment based on the PPS and (2) a pattern-mixture model (PMM) approach ([Table 8](#)). Unless otherwise specified, for subjects who receive IOP-lowering rescue therapy, any IOP values collected after the receipt of rescue therapy will be censored (i.e., treated as missing) in the analyses.

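### The confirmatory models pool children with adults, leave out the age stratum used in randomisation, and no planned analysis gives a single adults-only treatment difference

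*SAP*

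**What the plan says.** Protocol 9.4 stratifies the randomisation: "Two strata will be constructed based on age", with the cut at 18 years. SAP 3.2 repeats this. The sample size in SAP 3.3 refers to adults only: "approximately 400 adult subjects in total (200 subjects per treatment arm) will provide 90% power". Up to 30 children are enrolled in addition.

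SAP 8.1.1.1.1 names the confirmatory analysis set: "The primary analysis of the primary efficacy endpoint will be performed using a MMRM of IOP based on the FAS". That set has no age restriction. SAP 5.3 reads "The Full Analysis Set (FAS) will include all randomized subjects who received at least one dose of study medication", with the further conditions of baseline and post-baseline IOP data. SAP 7.2 lists the FAS, adults and children as separate groups for demographics, so the FAS is not another name for the adults.

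The primary model in SAP 8.1.1.1.1 has treatment, visit and their interaction "as fixed effects, and baseline IOP at the scheduled timepoint as a covariate". SAP 6.1 gives the general rule: "In general, the inferential analysis of each IOP endpoint will adjust for the baseline IOP". The key secondary models in SAP 8.1.1.1.2 are built the same way. None has an age term.

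On separate analyses by age, SAP 8.1.1.1.1 says "The primary analysis will be repeated on pediatric subjects", and the first and third key secondary and the other secondary analyses get the same repeat. The second key secondary (baseline mean diurnal IOP below 25 mmHg) does not. SAP 8.1.1.2 states "The sensitivity analyses consist of two types: (1) assessment based on the PPS and (2) a pattern-mixture model (PMM) approach", run on the per-protocol set and the FAS, and adds a trimmed-mean analysis for the primary endpoint under certain conditions. The age subgroups in SAP 8.1.3 are under 18, 18 to under 65, and 65 or older.

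**The concern.** Two things are missing. The factor that structured the randomisation is not in the model, which can cost precision. And the population to which the stated power refers never gets a treatment difference and confidence interval of its own.

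The second matters because the two strata differ by design. Adults must have 22 to 34 mmHg at all three baseline times and a corneal thickness within a set range, and are measured by Goldmann tonometry under a fixed procedure. Children need only an IOP that the investigator judges to require medication, may have congenital or secondary glaucoma, and may be measured with other tonometers. The documents give no paediatric treatment effect, SD or mean IOP. If the children's treatment difference departs from the adults', the pooled estimate moves towards it, in either direction, and no planned output shows directly whether the conclusion holds in adults.

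The point is sharper for the second key secondary endpoint. Children have no 22 mmHg floor, so their share of the below-25 mmHg subset may exceed their share of the trial.

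**Working it through.** **The plan's own figure.** Inputs from SAP 3.3: 200 adults per arm, SD 4.0, true difference 0, margin 1.5 mmHg, two-sided 5%, correlation 0.6, power 90%. The formula behind the 90% is not given, so several readings were tried.

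- One time point: SE = 4 × √(2/200) = 0.400; power = Φ(1.5/0.400 − 1.96) = 96.3%.
- Three time points of one visit, all upper limits ≤1.5 (simulation): 91.6%.
- All nine ≤1.5, no baseline adjustment (simulation): about 84%; with the requirement of ≤1.0 at five or more added, 72.4%.
- Full rule with baseline adjustment, assuming correlation 0.6 also with baseline (residual SD 4 × √(1 − 0.36) = 3.2; residual correlation (0.6 − 0.36)/(1 − 0.36) = 0.375): 94.2% with no loss, 90.5% with an assumed 10% loss.

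So 90% can be reached, under choices that the plan does not state. It is not disputed here. What matters is that it refers to adults.

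**Share of children.** p = 30/430 = 0.0698. With 20 children p = 20/420 = 0.0476; with 10, p = 10/410 = 0.0244.

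**Cost of omitting the stratum.** Let g be the child-adult gap in mean IOP that baseline IOP does not explain (assumed). Without the stratum the residual variance rises from 16 to 16 + p(1 − p)g², so

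SE inflation = √(1 + p(1 − p)g²/16) − 1.

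| Assumed gap (mmHg) | Nothing absorbed by baseline | Half absorbed |
|---|---|---|
| 3 | 1.8% | 0.5% |
| 4 | 3.2% | 0.8% |
| 5 | 4.9% | 1.3% |

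The pooled SE with the stratum is 4 × √(2/215) = 0.386. Without it, and with nothing absorbed, it is 0.393, 0.398 and 0.405. Adults alone give 0.400. If children had an SD of 6 or 8 mmHg (assumed), the pooled SE would be 0.402 or 0.424.

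**Effect of pooling on the estimate.** Pooled difference = (1 − p) × adult difference + p × child difference. Each 1 mmHg by which the children depart from the adults therefore moves it by about 0.07 mmHg, and 3 mmHg by 0.21.

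**Illustration at one time point.** Set the adult difference at the 1.5 mmHg margin. The chance that the upper limit is ≤1.5 is Φ((1.5 − pooled difference)/SE − 1.96). With 30 children and child differences of 0, 1.5 and 3, the pooled differences are 1.395, 1.500 and 1.605.

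| Children | SE | Child difference 0 | 1.5 | 3 |
|---|---|---|---|---|
| 30 | 0.386 | 4.6% | 2.5% | 1.3% |
| 20 | 0.390 | 3.8% | 2.5% | 1.6% |
| 10 | 0.395 | 3.1% | 2.5% | 2.0% |

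The full rule requires all nine limits, so the figure for one time point is an upper bound on the chance of passing overall. If adults were worse by 1.5 mmHg at all nine time points and children by 0, the full rule would pass about 0.01% of the time (400,000 simulated trials, SD 4, correlation 0.6).

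**The below-25 mmHg subset.** If half the adults and between half and all of the children qualify (assumed), children make up 15/215 = 7% to 30/230 = 13%.

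**The case against.** The strongest reply is that nothing is broken. The primary objective covers all subjects with glaucoma or OHT, so the pooled set is the right one. In the illustration with a child difference of 0, the true pooled difference of 1.395 lies inside the margin, so passing is not a false claim about that population. Stratified 1:1 allocation keeps the comparison unbiased whether or not the stratum is modelled. The 400 adults are still enrolled, and pooling at equal SD lowers the SE from 0.400 to 0.386. All of this stands, and it is why the pooled FAS should remain confirmatory.

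A second reply is that adults are already visible. The SAP plans paediatric repeats and two adult age bands, allows further subgroup analyses, and an adult point estimate can be approximated as (pooled − p × child)/(1 − p). This stands in part. The approximation gives no confidence interval, and non-inferiority is judged on the upper limit. Permission to add subgroups is not pre-specification, and an adult analysis chosen after unmasking carries less weight. The note in Protocol 14.3 that children may be analysed separately does not take them out of the FAS.

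Third, the size rests on assumed inputs, 30 is a ceiling, and every model adjusts for baseline IOP, so the lower column of inflation figures is the more plausible. That is fair. The appendix with the model code is also not in the text available here, so the reading of the model rests on the SAP prose, which lists the terms without age.

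**Conclusion.** The concern holds on all three facts: children are pooled into the confirmatory models, the randomisation stratum is not modelled, and no planned analysis gives one adults-only difference with its interval. The consequence is modest. At the enrolment ceiling the children's weight is 7.0%. The likely precision loss is about 1% (0.5% to 1.3% with half the assumed gap absorbed by baseline, 4.9% at the worst considered). The shift in the estimate is about 0.2 mmHg even if child and adult differences are 3 mmHg apart. These figures assume an SD of 4 in both strata and a child-adult gap that the documents do not give, and they shrink if fewer children enrol. It is a worthwhile, low-cost improvement to robustness and reporting.

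**What to change.** Keep the pooled FAS as the confirmatory analysis and make two additions to the SAP before unmasking.

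1. Add the randomisation stratum (adult or paediatric) as a fixed effect in the pooled primary and key secondary MMRMs. Carry it into the pattern-mixture runs, both in the imputation model of step a and in the MMRM of step c.
2. Pre-specify an adults-only repeat of the same MMRMs as a sensitivity analysis beside the planned paediatric repeat, without the stratum term, which is constant there. Include the below-25 mmHg endpoint.

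The cost is SAP wording, one extra model term and a rerun of existing code: three primary time-point models, one diurnal model serving both Week 1 and Month 3, and three subset models. It needs no new data or subjects and does not change the testing sequence in SAP 6.4.
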